Aim 1. Acceptability: To examine feasibility and acceptability of lower extremity neuromodulation in patients at risk of ICUAW. H1.1: The adherence to daily use of lower extremity neuromodulation is more than 80% among the IG. Adherence is defined as the use of lower extremity neuromodulation at least one hour per day for at least 4 days per week. H1.2: The perceived acceptability, and perceived benefit would be high among IG.

Aim 2. Proof of concept effectiveness: To examine effectiveness of lower extremity neuromodulation for intubated patients at risk of ICUAW H1.1: E-Stim will improve motor function including muscle endurance and thickness, nerve conductivity and amplitude, by utilizing objective assessments (surface electromyography, ultrasound, dynamometry), after 4 weeks of application or hospital discharge, whichever comes first. H1.2: E-Stim will improve lower extremity nerve function and tissue perfusion after 4 weeks of application or until hospital discharge, whichever comes first. The nerve function parameters will be measured with assessed with a digital test (DPN Check) for peripheral neuropathy and the perfusion parameters will be assessed using a near infrared spectroscopy using a validated imaging system (Kent Imaging System).

Section E: Protocol Risks/Subjects

E1. Risk Category

Category 1: Research not involving greater than minimum risk.

E2. Subjects

Gender:

Both

Age:

Adult (18-64 yrs), Geriatric (65+ yrs)

Ethnicity:

All Ethnicities

Primary Language:

English, Spanish

Groups to be recruited will include:

Patients

Which if any of the following vulnerable populations will be recruited as subjects?

Cognitively impaired

Vulnerable populations require special protections. How will you obtain informed consent, protect subject confidentiality, and prevent undue coercion?

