E4. Neonates

Will neonates of uncertain viability or nonviable neonates (as described in 45 CFR 46 Subpart B) be enrolled in the research?

No

E5. Children

Will children be enrolled in the research?

No

Section F: Design/Procedure

F1. Design

Select one category that most adequately describes your research:

c) Pilot

Discuss the research design including but not limited to such issues as: probability of group assignment, potential for subject to be randomized to placebo group, use of control subjects, etc.

We will prospectively recruit 40 patients at risk of ICUAW. Sample size is convenient and designed to explore acceptability and feasibility of objective tools for measurement. Eligible participants will be screened at BSLMC. Those who satisfied the inclusion and exclusion criteria and signed the informed consent form will be randomly assigned with ratio of 1:1 into two groups. Consenting will be performed with a legal authorized representative (LAR) that is present. When the subject regains consciousness and is aware in time, space, and person, he/she will be re-consented. If the subject decline to continue participation in the study, the subject will be withdrawn. The informed consent will be obtained from all participants and their LAR.

Sub-population: Post-surgical patients that are admitted to the ICU will be consented either before surgery, or by a LAR on the day of surgery as described above.

The study will be double-blinded (clinicians and patients) in intervention (IG) and control (CG) group. Both cohorts will be followed-up and monitored at 3 days, and then weekly for a total period of 4 weeks or until hospital discharge, whichever comes first. • Intervention group (IG). The IG (n=20) will be undergoing E-Stim therapy with an active device during the hospitalization period until 4 weeks or discharge, whichever comes first. To deliver E-Stim, 2 electrodes will be placed in each proximal gastrocnemius and Achilles tendons. • Control Group (CG). The CG (n=20) will be undergoing E-Stim therapy with a placebo device (5-10% currents) as described in the IG.

Inclusion Criteria:

-Any patient older than 18 years old admitted to the ICU within two days. -Patient can be intubated with ventilatory assistance or not.

Exclusion Criteria:

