Neuropathy test: Sural nerve conduction/amplitude assessment (neuropathy, DPNCheck Device by Neurometrix Inc)

Biomarkers tests: Creatinine kinase, C-reactive protein, creatinine, potassium, myosin, serum lactate, arterial SpO2, duplex ultrasound for DVT will be collected from the electronic medical records. If biomarkers were not collected as a standard/regular procedure in the ICU; data will not be extracted from the electronic medical records. Research staff will not draw any blood samples.

Then, the patients will receive an individually programmed device to deliver neuromodulation to both gastrocnemius muscles simultaneously. The frequency of therapy will be 1 hour daily, and the duration will be up to 4 weeks or until hospital discharge, whichever comes first.

The coordinator will provide the ICU staff with a weekly spreadsheet showing utilization (therapy sessions/day) so compliance can be monitored. Also, the devices will monitor the time of usage to confirm hours of effective neuromodulation therapy to the skin.

Follow-up assessments will be performed at 3 days, and then weekly until 4 weeks or until hospital discharge, whichever comes first, by the research staff. The follow-up assessment will be identical to the baseline assessment.

In the final visit, we will assess muscle strength (ankle dynamometer, RoMech Digital Hanging Scale).

Additional measurements: - 1-month post-hospital discharge phone questionnaires: instrumental activity of daily living scale (IADL), community engagement (the Life Space Questionnaire), independence in daily living activities (KATZ), and anxiety (BAI).

Section G: Sample Size/Data Analysis

G1. Sample Size

How many subjects (or specimens, or charts) will be used in this study?

Local: 40 Worldwide: 40

Please indicate why you chose the sample size proposed:

Sample size is convenient and selected based on available resources to demonstrate feasibility and the proof of concept effectiveness of neuromodulation therapy for patients admitted to ICU and post-ICU. We plan to recruit 40 eligible subjects.

G2. Data Analysis

Provide a description of your plan for data analysis. State the types of comparisons you plan (e.g. comparison of means, comparison of proportions, regressions, analysis of variance). Which is the PRIMARY comparison/analysis? How will the analyses proposed relate to the primary purposes of your study?

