Statistical Design: Independent t-test, U-test, or Chi-square (depends on type of variables) will be used to compare between groups (IG, and CG for key baseline descriptors including demographics and relevant clinical characteristics). Those descriptors which showed statistical significant difference will be considered as covariates for adjusting the results in the following assessments. Appropriate mixed models (linear for continuous or Generalized Estimating Equations (GEEs) for non-continuous or non-parametric variables) will be used to test the intervention effect for each of the primary or secondary outcomes. Results will be adjusted by covariates as described above.

P-values of 0.05 or less will be considered statistically significant based on a two-sided test unless otherwise noted. All variables will be tabulated descriptively at each scheduled time point (baseline, follow up and discharge date). For each continuous variable, the analyses will include the mean, standard deviation, minimum and maximum. For each categorical variable, the summary will include frequencies and percentages. Each variable will be analyzed using all available data. Baseline variables will be summarized using descriptive statistics. We assume that a successful intervention is also helpful to maintain subjects muscle mass, reduce neuromyopathy signs and increase perfusion. The measured parameters (e.g. sEMG, US, strength, Kent imaging, DPN Check, etc.) should change substantially from baseline to the end of the intervention. For example, the EMG amplitude values should show increased voltages. Next, for all continuous variables, pre-treatment scores will be regressed on post-treatment scores to form residualized change scores (e.g. sEMG, US, strength, Kent imaging, DPN Check, etc.). Correlations will then be generated among these scores to determine whether changes in sEMG factors are related appropriately with increases in (clinically assessed) functional capacities and self-report measures of activities at 1 month post-hospital discharge. ANOVA test will be used to examine significant difference between patients with severe risk factors for prolonged ICU stage (e.g. age, BMI, cardiovascular morbidities). Moderator effects will also be examined for exploratory purposes.

Section H: Potential Risks/Discomforts

H1. Potential Risks/Discomforts

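### Aim 1 H1.2 judges perceived benefit in the active arm alone, with no stated comparison with the blinded sham arm, so a placebo response cannot be told apart from benefit of the active current

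*Combined protocol and SAP*

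**What the plan says.** Section D, Aim 1 has two hypotheses, and both name the intervention group only. H1.1: "The adherence to daily use of lower extremity neuromodulation is more than 80% among the IG". H1.2: "The perceived acceptability, and perceived benefit would be high among IG".

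F1 sets up a matched comparator. Patients are "randomly assigned with ratio of 1:1 into two groups", and patients and clinicians are both blinded. "The IG (n=20) will be undergoing E-Stim therapy with an active device", and "The CG (n=20) will be undergoing E-Stim therapy with a placebo device (5-10% currents) as described in the IG".

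G2 says that mixed models or GEEs "will be used to test the intervention effect for each of the primary or secondary outcomes". Section I repeats this. G2 also promises that all variables will be tabulated descriptively at each time point, but does not say by arm.

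On device use, F2 describes a weekly utilization sheet for ICU staff and adds: "Also, the devices will monitor the time of usage to confirm hours of effective neuromodulation therapy to the skin". Neither record is limited to the IG.

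**The concern.** Perceived benefit is a subjective rating. Blinded patients who receive a daily device session for up to four weeks may report benefit because of attention, expectation or natural recovery. A high rating among IG patients contains all of these as well as any effect of the current. Only the sham arm can separate them, and the stated hypothesis does not use it.

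At stake is the wording of one Aim 1 conclusion. As written, the trial could report high perceived benefit for a device that patients rate no better than sham, and a reader would naturally credit the rating to the stimulation.

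**Working it through.** **1. The plan's own figures.** The sample of 40 is a convenience sample (G1) with no effect size, event rate or power, so there is no calculation to reproduce. The allocation is consistent: 40 / 2 = 20 per arm, as F1 states.

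**2. Is an Aim 1 measure covered by a between-arm analysis?** Setting the sections side by side:

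- F2 lists sEMG endurance and muscle thickness as primary, and perfusion as secondary, followed by the DPNCheck and biomarker tests.
- Section I lists sEMG and DPNCheck as primary, and perfusion and biomarkers as secondary.
- The two lists differ, but adherence, acceptability and perceived benefit are on neither. The models in G2 and Section I therefore do not reach them.
- For perfusion, F2 says outright that placebo and active devices will be compared. Nothing similar is said for any Aim 1 measure.
- The one-month telephone instruments in F2 are IADL, Life Space, KATZ and BAI. None is described as measuring acceptability or perceived benefit of the device.

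So no comparison of perceived benefit is stated. It is also not ruled out.

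**3. What would a by-arm comparison deliver?** The counts below are illustrative assumptions: a yes/no rating of benefit per patient, with the stated number of respondents per arm. The method is the Newcombe interval, built from a Wilson interval (l, u) for each arm:

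- Wilson limits: [x + z²/2 ± z·√(n·p·(1−p) + z²/4)] / (n + z²), with z = 1.96.
- Lower limit of the difference: d − √[(p₁ − l₁)² + (u₂ − p₂)²].
- Upper limit of the difference: d + √[(u₁ − p₁)² + (p₂ − l₂)²].

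*All 20 per arm respond, 17/20 v 17/20.* Wilson limits are 0.640 to 0.948 in each arm. The half-width is √[(0.850 − 0.640)² + (0.948 − 0.850)²] = 0.232. The difference is 0, with a 95% CI of −23 to +23 points.

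*All 20 per arm respond, 17/20 v 10/20.* Wilson limits for 10/20 are 0.299 to 0.701. The difference is +35 points. Lower limit: 0.35 − √[(0.850 − 0.640)² + (0.701 − 0.500)²] = 0.059. Upper limit: 0.35 + √[(0.948 − 0.850)² + (0.500 − 0.299)²] = 0.573. The 95% CI is +6 to +57 points.

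*Only 10 per arm can respond, 9/10 v 9/10.* Wilson limits are 0.596 to 0.982. The half-width is √[(0.900 − 0.596)² + (0.982 − 0.900)²] = 0.315, so about ±32 points.

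*If the rating is a continuous score.* The half-width in SD units is t × √(2/n). With 20 per arm, 2.024 × √(2/20) = 0.64 SD. With 10 per arm, 2.101 × √(2/10) = 0.94 SD.

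The case of 10 respondents matters because the background text before Section D says that measures needing patient awareness were hard to obtain in this setting.

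**4. What cannot be computed.** H1.2 has no instrument, scale, time point, respondent or cut-off. The chance that perceived benefit is declared high when the device adds nothing over sham therefore has no defined value.

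**The case against.** The strongest reply is that this is a labelled pilot whose effectiveness question belongs to Aim 2. Aim 2 uses objective measures with between-arm models, and no section uses perceived benefit as evidence of efficacy. That stands, and it limits the consequence to how one Aim 1 result is worded. It does not make an uncontrolled benefit rating interpretable.

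A second reply is that the contrast will usually be inconclusive with 20 or fewer per arm, and that a sham at 5-10% currents is not inert. Both parts are true. They are reasons to report an interval and read it cautiously, not to leave out the comparator.

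Three stronger readings are tempting, and the documents do not support them.

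- *A reader might infer that the IG-only adherence target is itself wrong, because it mixes ward delivery with tolerance of the current.* H1.1 defines adherence purely as use: "Adherence is defined as the use of lower extremity neuromodulation at least one hour per day for at least 4 days per week". The plan never reads it as tolerance. Staff time and procedures are a legitimate part of whether daily use in an ICU is feasible, and an active-arm target is a normal pilot criterion. The same holds for acceptability, which is an absolute question about the active device.
- *A reader might infer that the plan excludes any comparison with sham on Aim 1.* It is only silent. The usage records in F2 are not limited to the IG, and nothing prevents CG figures from being reported.
- *A reader might want a false-success rate for H1.2.* That would mean borrowing the 80% figure from H1.1, dichotomising an undefined measure and assuming that all 20 patients per arm answer. Setting the result beside a superiority test would also compare two different questions.

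**Conclusion.** The point holds for perceived benefit in H1.2. The hypothesis concerns the active arm alone, no section states a sham comparison for it, and a placebo response therefore cannot be separated from benefit of the active current. It does not hold as a fault in the adherence target or in an absolute acceptability rating, which are reasonable feasibility criteria as they stand.

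The improvement is modest and cheap. The resulting estimate is imprecise, with a half-width of roughly 23 points with 20 respondents per arm and 32 points with 10, on the illustrative counts above. Because the sham carries some current, similar ratings would not show that the active current has no perceived effect. The missing instrument and cut-off for H1.2 is a separate gap that has to be closed first.

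**What to change.** In Section D (Aim 1) and G2:

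- Put the same perceived-benefit question to both arms at the same visit. Report the IG minus CG difference with a 95% CI and the number who answered in each arm.
- State that perceived benefit will be attributed to the active device only from that contrast, and that the contrast is descriptive. An interval that includes zero is to be called inconclusive, not evidence of no benefit.
- Keep the IG adherence target above 80% and an absolute IG acceptability rating as the feasibility criteria.
- Report device-logged CG adherence, by the same rule, beside the IG figure. This is descriptive context on whether any shortfall is shared by both arms.

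The cost is a few sentences. By-arm adherence should need no new data, since F2 does not limit usage logging to the IG. The benefit question must be defined for the IG in any case, and asking it in the CG as well adds little and helps protect the blind. The downside is that the perceived-benefit result will carry a wide interval and may look less favourable than an IG-only rating.

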In ICUAW, affection to the lower extremity can be seen in 32.3%. Mainly due to prolonged periods of immobilization or sedation, that lead to atrophy and dysfunction in the quadriceps and gastrocnemius muscles. The consequences are reduced 6-minute walk test distance, reduced ability to perform activities of daily living, and reduced ability to return to driving and paid employment. In healthy individuals, strict bed rest causes a 1% decrease in muscle strength per day. Casting limbs such as in orthopedic injuries has been shown to result in 25% decrease in muscle strength in 7 days. Therefore, in ICU patients, this problem should be approached as prompt as admission. A recent systematic review (Qin ES et al) in 10 studies (n = 985) found that early mobilization decreased the incidence of ICUAW at hospital discharge, increased the number of patients who were able to stand, and increased the number of ventilator-free days during hospitalization. However, reduced hospital staff or increased burden can be a limitation for providing assisted mobilization.

A practical solution to address these limitations is the use of electrical stimulation (E-Stim). In this matter, AVAZZIA Inc. (Dallas, TX, USA) has created an E-Stim device (Tennant Biomodulator PRO) that works on a high voltage alternative pulsed current (HVAPC) to address lower-extremity muscle weakness, endurance, pain, and neuropathy. This technology works through a symmetric biphasic waveform that achieves deep stimulation of the muscle fibers. In our previous trial in ICU COVID-19 patients (NCT04685213, H-47781-A), we demonstrated HVAPC improves gastrocnemius muscle endurance without burnout of oxygen consumption. Other ICU studies (Nussbau et al.) have demonstrated E-Stim is feasible to preserve strength and muscle mass, and reduce muscle degradation leading to maintenance of functional capacity. Its benefit has been seen to be higher when placed in hams and calf muscles bilaterally, in a supine position, and administered 5-7 days a week or until extubation or hospital discharge. Another benefit has been linked to neural adaptations.

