The risk to participants due to the optional assessments and surveys is considered minimal because all that is required is simple walking and balance movements in a controlled environment with an attendant present. This research routine will not place subjects at higher risk than normal activities of daily living, and no more risk of harm or discomfort is associated with these tests than the discomfort normally incurred while performing normal muscle stretching. Subjects will be allowed rest time between trials as needed.

Potential risk to the subject due to the pulse oximeter optional test is considered minimal; this device is non-invasive, non-toxic, and non-ionizing. The device will be placed on the subject's finger, and monitor their oxygen levels.

H2. Data and safety monitoring plan

Do the study activities impart greater than minimal risk to subjects?

No

H3. Coordination of information among sites for multi-site research

Is the BCM Principal Investigator acting as the SPONSOR-INVESTIGATOR for this multi-site research?

No or Not Applicable

Is BCM the COORDINATING CENTER for this multi-site research?

No or Not Applicable

Section I: Potential Benefits

Describe potential benefit(s) to be gained by the individual subject as a result of participating in the planned work.

There is potential benefit of prevention or improvement of hospital acquired weakness due to ICU stay, based on previous studies the neuromodulation therapy will improve blood flow, tissue perfusion and muscle activation. In addition, the participation in this study may help the investigators better understand the prevention of ICU-acquired weakness and post-ICU syndrome and may determine if this therapy has an impact in daily leaving and activities after getting discharged from the hospital.

Primary outcomes include myopathy (sEMG) and neuropathy (DPN Check) assessment. Secondary outcomes include perfusion (Kent Imaging), and biomarkers. This therapy will also help to determine if hospital length of stay, and time for extubating can be reduced (patient health record). The primary and secondary outcomes will be assessed at baseline, 3 days, and then weekly after completing 4 weeks or until hospital discharge, whichever comes first. Appropriate mixed models (linear for continuous or Generalized Estimating Equations (GEEs) for non-continuous or non-parametric variables) will be used to test the intervention effect for each of the primary or secondary outcomes.

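### Aim 2 places the effect at week 4 or discharge, a patient-specific day that therapy may shift, and the model names neither a time scale nor a contrast day

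*Combined protocol and SAP*

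**What the plan says.** Section D, Aim 2, expects improvement in motor function, nerve function and perfusion "after 4 weeks of application or hospital discharge, whichever comes first". Section F2 sets the schedule: "Follow-up assessments will be performed at 3 days, and then weekly until 4 weeks or until hospital discharge, whichever comes first". Treatment stops at the same point. Ankle dynamometry is listed in F2 for the final visit only and is not among the baseline measurements.

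Section G2 tests the intervention effect on each primary and secondary outcome with a linear mixed model, or GEE for other variable types, at two-sided 0.05 on all available data. It does not say whether time enters as days or as visit labels, on which day the arms are compared, or how discharge before week 4 is handled. It also says "All variables will be tabulated descriptively at each scheduled time point (baseline, follow up and discharge date", and that the measured parameters "should change substantially from baseline to the end of the intervention".

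Section I adds: "This therapy will also help to determine if hospital length of stay, and time for extubating can be reduced". The background in Section C gives two rates of loss: "In healthy individuals, strict bed rest causes a 1% decrease in muscle strength per day" and "Casting limbs such as in orthopedic injuries has been shown to result in 25% decrease in muscle strength in 7 days".

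**The concern.** The day on which a patient reaches the Aim 2 endpoint is fixed after randomisation, by discharge. The protocol itself asks whether therapy brings discharge forward, and its background describes strength as falling with each day of immobility. If active patients leave sooner, they are measured after fewer days of loss. They can then look better preserved at the end of stay even if their muscle declines at the same daily rate.

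Randomisation does not remove this, because the imbalance would be a consequence of treatment. At stake is whether a positive Aim 2 result means slower muscle loss or only an earlier measurement.

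**Working it through.** The plan has no figure to reproduce here. The 40 patients are a convenience sample, and no power, effect size, SD or length of stay is given.

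**Inputs from the documents:** 20 per arm; two-sided 0.05; follow-up capped at 28 days; loss of 1% per day (bed rest), or 25 / 7 = 3.6 points per day (casting, if linear).

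**Assumed inputs:** control stay 14 days on average; active stay 0, 3 or 5 days shorter; gamma-distributed stay with shape 2 to 4, bounded to 3-28 days; daily loss with a 40% between-patient coefficient of variation and the same mean in both arms; measurement SD of the change 3 points, varied to 8 and 10.

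**Step 1: size of the artefact.** Spurious difference = daily loss × difference in mean stay. At 1% per day, 3 days gives 3 points and 5 days gives 5. Bounding the stay trims this slightly. With shape 4 the mean stays become 13.80, 10.99 and 9.03 days, so the differences are 2.8 and 4.8 points.

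**Step 2: one case by hand (shape 4, 1% per day, 3 days shorter).** Variance of change = variance of stay + 0.16 × mean squared stay + 9.
- Control: stay SD 6.40, so 41.0 + 0.16 × 231.4 + 9 = 87.0.
- Active: stay SD 5.35, so 28.6 + 0.16 × 149.4 + 9 = 61.5.
- Standard error = √((87.0 + 61.5) / 20) = 2.73, and 2.8 / 2.73 = 1.03. With 38 degrees of freedom this gives rejection in about 17% of trials.

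**Step 3: simulation, t-test on change at end of stay, 10,000 null trials per setting, 1% per day.**

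| Measurement SD | Equal stays | 3 days shorter | 5 days shorter |
|---|---|---|---|
| 3 | 5% | 12-17% | 28-44% |
| 8 | 5% | 10-12% | 20-26% |
| 10 | 5% | 9-10% | 16-21% |

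Ranges are over gamma shapes 2 to 4. At the casting rate with SD 3 the figures are 13-18% and 32-50%, so the two rates together span roughly 12-18% and 28-50%. The casting rate run linearly to day 28 would mean 100% loss, so it is an outer bound only. A comparison at day 3 stayed near 5% in every 1% per day setting.

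**Step 4: does the choice of model matter?** I used the same null at 1% per day, with visits at baseline, day 3, weekly and discharge (shape 4, measurement SD 3, 150 runs, so imprecise). Stays were 14 and 9 days.
- Last visit coded as a common final visit: rejected in 44% of runs (4% with equal stays).
- Actual days since baseline, effect as difference in slope: rejected in 6% (6% with equal stays).

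Both are mixed models, and G2 as written allows either.

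**The case against.** The strongest reply is that the planned test is longitudinal. G2 uses mixed models or GEE on repeated visits and reserves the t-test for baseline descriptors. F2 describes, for perfusion, a comparison of each time point with baseline and between groups. A reader might infer from Aim 2 and G2 that the sponsor has committed to an end-of-stay arm test. The documents do not support that. The discharge date appears in a sentence on descriptive tabulation, the sentence on change to the end of the intervention states an expectation, and the residualized change scores feed correlations. The rejection rates in Step 3 therefore illustrate one permitted analysis and are not the error rate of the plan. What survives is that G2 leaves the time scale and contrast day open, while Aim 2 points to the end of stay.

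A reader might also infer that bias has been shown. It has not. It needs stay to differ by arm, and a reduction of 3 to 5 days out of 14 is 21 to 36%. Length of stay is raised once, under potential benefits, and is not a listed primary or secondary outcome.

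The background rates are for strength in healthy or casted people. The documents give none for thickness, sEMG or nerve conduction. If muscle recovers before discharge, the distortion could run the other way.

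The pilot label lowers the stakes, but the plan still tests effectiveness at 0.05.

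**Conclusion.** The point holds as a conditional weakness in how the Aim 2 effect is defined. As worded, the effect sits at a day that treatment may change, and the model section does not correct this. If stays are equal, nothing is lost. If active stay is 3 or 5 days shorter, an end-of-stay comparison would reject in roughly 12-18% or 28-50% of null trials under the SD 3 assumptions, and less with noisier measurement. These sizes rest on assumed stay, spread and measurement error, and on carrying strength-loss rates over to other outcomes. Outcomes measured at day 3 and weekly can be protected by specifying the analysis. Final-visit strength cannot, because F2 schedules no earlier value.

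**What to change.** In Aim 2 and G2:

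1. Enter every assessment, including the one at discharge, at its actual day since baseline in the mixed model or GEE, with the baseline value.
2. Define the arm effect either as the difference in change per day or as the difference at one prespecified scheduled day common to both arms. The per-day version assumes roughly linear change. The common-day version does not, if time is modelled flexibly.
3. Keep patients discharged before that day in the model through their earlier measurements, and state how death is handled. Analysing only those still in hospital would select on a post-randomisation event.
4. Report length of stay by arm.
5. Treat end-of-stay contrasts, including final-visit strength, as descriptive.

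This needs wording only, since the day-3 and weekly visits are already scheduled. The costs are that patients who leave before the chosen day contribute only earlier measurements, and that final-visit strength supports no causal comparison of arms. An early common day keeps more patients but covers less of a treatment lasting up to 4 weeks. The documents give no stay data to settle that choice, so the sponsor should make it and give the reason.
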